DIBH qualified patient will experience one high-resolution CT scan as SOC and additional lower dose CT scans to further investigate inter-DIBH patient surface and tumor position stability and repeatability.

1. Spirometer will be used to select DIBH level and monitor DIBH status during CT simulation. One SOC high-resolution CT will be acquired in single DIBH duration. Within 10 minute, a low-resolution/low-dose CT image in single DIBH duration will be acquired. This study is to quantify inter-DIBH tumor position and patient surface repeatability.
2. Patient will then be scanned using a lower dose CT protocol with DIBH level set at $\pm 10\%$ deviated from the selected DIBH level. This study is to find the correlation between DIBH level and tumor position /chest-abdomen surface level.

The SOC DIBH CT scan will be transferred to Eclipse treatment planning system for treatment planning. Tidal volume measured by spirometer and DIBH surface from CT image will be used as a reference surface for patient treatment initial setup. CBCT will be acquired before each fractional treatment for the patient alignment before beam delivery.

During the treatment delivery, patient will perform DIBH while AlignRT system monitors patient surface. As a pilot study, we will also use spirometer to monitor patient breath-hold tidal volume, and imaging acquired in any two DIBH periods to quantify inter- and intra- DIBH tumor position variation. Following our SBRT treatment protocol, patient will get CBCT scan before the last beam delivery. We will follow the same protocol to acquire CBCT images. These CBCT images will be used to evaluate treatment dose variation to quantify treatment delivery accuracy.

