5.2.2 Tumor motion evaluation and target volume delineation

On the acquired four different DIBH CTs, gross tumor volume (GTV) will be contoured by an appropriately trained physician. Tumor center point (center of mass) will be the identified and used for motion evaluation. Both inter- and intra- motion amplitude will be analyzed and margins will be estimated. The acquired high-resolution DIBH CT will be used as a primary image for planning. Physician will expand the GTV to PTV by adding proper size margins.

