6.1 Study Design/Study Endpoints

A single-center prospective pilot study will be conducted according to the schema outlined at the beginning of this document. Informed consent will be obtained from 10 thoracic or abdominal cancer patients, each to be treated with SBRT technique. In order to quantify tumor motion/surface stability and repeatability during VRT-DIBH, several CT images will be acquired during treatment simulation, as well as CBCT and VRT surface images during treatment delivery. The designed study aims to explore the geometry and dosimetry accuracy of VRT-DIBH in thoracic or abdominal cancer SBRT.

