6.3 Data Analyses Plans

All recorded CBCT images will be used for tumor and critical organs geometry accuracy study by exporting to Velocity software. PTV and critical organs will be delineated. Tumor position accuracy will be evaluated. Further delivered dosimetric accuracy will be evaluated with through dose calculation on acquired CBCT images.

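### Does section 5.2.2 let the two ±10% breath-level CTs count as repeats, and read within-hold motion off scans taken in one hold each?

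*Combined protocol and SAP*

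**What the plan says.** Section 5.2.1 sets out four simulation CTs per patient: the planning scan, one low-dose scan repeated at the same breath level, and two low-dose scans at levels 10% above and below it. Section 5.2.2 reduces each CT to a tumor center of mass and continues: "Both inter- and intra- motion amplitude will be analyzed and margins will be estimated". It does not separate same-level from off-level scans there, and it names no other images. Its last sentence is about the physician's planning expansion.

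Section 4.1 describes the same scans in more detail. Its lead-in speaks of "additional lower dose CT scans to further investigate inter-DIBH patient surface and tumor position stability and repeatability". A two-item list follows, and each item states its own purpose. Item 1, the planning CT plus the same-level repeat: "This study is to quantify inter-DIBH tumor position and patient surface repeatability". Item 2, the ±10% scans: "This study is to find the correlation between DIBH level and tumor position", and likewise for the surface level.

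Motion within a hold is also covered in 4.1. Item 3 of the training list assigns positions recorded during one hold to intra-DIBH stability, and positions recorded over several holds to inter-DIBH repeatability. During treatment, 4.1 adds "imaging acquired in any two DIBH periods to quantify inter- and intra- DIBH tumor position variation".

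Section 6.1 is general: "In order to quantify tumor motion/surface stability and repeatability during VRT-DIBH, several CT images will be acquired during treatment simulation". Section 6.3 covers only the cone-beam images: "All recorded CBCT images will be used for tumor and critical organs geometry accuracy study by exporting to Velocity software". The target margin is a secondary objective (2.2.1) and a listed endpoint (2.4.2).

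**The concern.** Two things look wrong.

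First, the 4.1 lead-in gives the additional scans, in the plural, a repeatability purpose. Only one low-dose scan is at the same level, so the plural seems to take in the ±10% scans. Section 6.1 also ties the simulation CTs to repeatability without a split by level, and 5.2.2 lists all four just before it mentions margins. An analyst who treated all four as repeats would add a breath-level change made on purpose to what the margin objective calls residual motion. Another analyst, following item 2, would not. The two could report different inter-DIBH figures from the same patients.

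Second, 5.2.2 promises intra-DIBH amplitude but names only CTs. Of the planning scan, 4.1 says: "One SOC high-resolution CT will be acquired in single DIBH duration". The same-level repeat is also taken in one hold, and the ±10% scans are each set at their own level. One position per hold carries no information about movement during that hold.

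At stake is the study-level margin estimate. The margin a physician sets for an individual patient is a separate matter.

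**Working it through.** **Count of scans.** 1 planning + 1 same-level low-dose + 2 off-level = 4, which agrees with the four in 5.2.2.

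**What the four scans contain.** Relative levels are 0, 0, +10 and −10. They form 4 × 3 / 2 = 6 pairs: 1 pair at the same level, 4 pairs that differ by 10 and 1 pair that differs by 20. With the level set near 75% of maximum inspiration (4.1), the off-level scans sit at 0.75 × 0.9 = 67.5% and 0.75 × 1.1 = 82.5% if the 10% is relative, or at 65% and 85% if it means points of the maximum.

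**Within-hold information in the CTs.** 10 patients × 4 holds × (1 − 1) = 0 degrees of freedom. The CTs cannot give intra-DIBH motion, so that figure has to come from other imaging.

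**Effect of pooling, if anyone pooled.** Let s be the same-level SD and d the tumor shift per 10% step, equal and opposite on one axis. Both are assumptions, because the documents give neither. For positions e1, e2, e3 + d and e4 − d, the expected sample variance is s² + 2d²/3, so

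ratio of four-CT SD to s = √(1 + (2/3)(d/s)²).

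- d/s = 0: 1.00
- d/s = 0.5: 1.08
- d/s = 1: 1.29
- d/s = 2: 1.91

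If amplitude means peak-to-peak, the expected range of a same-level pair is 2s/√π = 1.128s. The expected range of four scans (by simulation) is 2.06, 2.23, 2.69 and 4.18 times s at the same d/s values. The ratios to the pair are 1.8, 2.0, 2.4 and 3.7, but 1.8 of that arises with no shift at all, from comparing four scans with two. The part due to the shift is 2.23/2.06 = 1.08, 2.69/2.06 = 1.31 and 4.18/2.06 = 2.03.

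**Would precision tempt an analyst to pool?** Same-level pairs give 10 × (2 − 1) = 10 degrees of freedom if all ten patients reach simulation, with a 95% interval for the SD of 0.70 to 1.75 times the estimate. Pooling gives a nominal 10 × 3 = 30 (0.80 to 1.34 times), but for an SD that also contains the level shift. The pairs are not the only source either: 4.1 adds positions over several holds at training and imaging in two holds at treatment. The second of these is not stated per fraction, so I put no total on the degrees of freedom.

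**Does the text direct pooling?**

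- 4.1 lead-in: a general aim for the additional scans, introducing the list.
- 4.1 item 1: same-level repeat, for repeatability.
- 4.1 item 2: ±10% scans, for the level–position relation.
- 5.2.2: both kinds of motion analyzed and margins estimated; no rule for combining scans.
- 6.1: a broad aim shared by CTs, cone-beam images and surface images; the ±10% scans are not mentioned.
- 4.1 training item 3 and the treatment paragraph: the imaging for intra-DIBH variation is named.

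No line says that the ±10% scans are repeats, and no line says that within-hold motion will be read from the CTs.

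**The case for a change.** The best case for a change is that 5.2.2 is where margins are mentioned, that it regroups all four scans without citing the split in 4.1, and that 6.3, where one would expect the rule, contains no margin analysis. The margin is a stated endpoint even in a pilot, and a clarifying sentence would need no extra scans.

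Part of this stands. Section 5.2.2 lacks a pointer to 4.1, and the inputs to the margin endpoint are not listed in one place.

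The rest is weaker. A lead-in followed by items that each state a purpose is read through its items. Two purposes for the simulation CTs also fit objective 2.2.2, which asks about sensitivity as well as stability and reproducibility. Section 5.2.2 is a pre-treatment step that ends with the planning expansion, so its margins may be the per-patient ones and not the study endpoint; the treatment imaging and cone-beam errors do not yet exist at that point.

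A tidy rule could also do harm. Confining the ±10% scans to the level correlation would rule out a defensible use, in which the level–position slope is combined with the level variation actually observed. A list of inter-DIBH inputs that left out the training-session positions would conflict with 4.1. And a list without a rule for combining sources would still let two analysts differ.

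**Conclusion.** No change follows. An analyst who follows 4.1 item by item keeps the ±10% scans apart from the repeats and takes within-hold motion from the imaging that 4.1 names, which is a sound analysis. The level of each scan is fixed by design, so the scans can always be sorted. What remains is missing detail that analysts fill sensibly: a cross-reference absent from 5.2.2 and an unwritten input list for a descriptive secondary endpoint.

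The inflation from pooling (1.08 to 1.91 times in SD for d/s from 0.5 to 2) is conditional on a step that the plan does not direct and on values that it does not give, so it is not an estimate of error in this trial. The conclusion assumes that the 4.1 items govern its lead-in and that intra- in 5.2.2 means within a breath-hold, as it does in 4.1.

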5.2.3 Critical organs delineation

SOC

5.2.4 Treatment planning

SOC

5.2.5 Daily treatment

- Patient will be positioned with vac lock bag in stereotactic body frame and setup with stereotactic coordinates recorded during simulation;
- Setup DIBH tidal volume use spirometer to reproduce simulated tidal volume;
- Initial setup patient position with AlignRT system using CT surface;
- Patient will receive a CBCT scan and align to simulated CT images;
- Right after CBCT alignment, AlignRT system will acquire a new surface image for treatment monitoring;
- Treatment delivery follows routine SBRT treatment, with one CBCT check before and one CBCT before last beam (not during treatment beam delivery).

5.2.8 Post-Radiation analysis

- Analyze recorded daily AlignRT treatment setup delta values
- Analyze recorded daily position shift using CBCT alignment
- Analyze recorded daily AlignRT treatment delta values, investigate surface stability and reproducibility
- Delineate tumor on recorded CBCT images and investigate the position error
- Project treatment beams on CBCT images and recalculate dose with CBCT images. Evaluate dose difference between the planned and the delivered.
- Treatment time analysis

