2.3 Exploratory Objectives

2.3.1 To quantify SBRT dose variation between planned and delivered with VRT-DIBH technique.

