5.2 Procedures during Treatment

5.2.1 CT simulation

- CT Simulation scans at DIBH will be assisted by spirometer ---must ensure tubing from spirometer not over chest wall so skin rendering is able to be reproduced.
- CT simulation scan (full-length) will be acquired with at a single DIBH duration, starting at least 10 cm above the superior extent of tumor and continuing on every CT slice to at least 10 cm below the inferior extent of the tumor. DIBH signal will be monitored by spirometer. If there is no contraindication to contrast administration, patient will receive DIBH CT scans with contrast administration.
- CT acquisition should be done with gantry 0 degree with spacing ≤ 2 mm.
- Additional DIBH CT scans will be conducted using lower dose CT scan protocol. One at the same DIBH level and the other two will be $\pm 10\%$ deviated from DIBH breath level

- All images will be transferred to the treatment planning computers for tumor motion evaluation and planning.

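### The planned-versus-delivered dose difference mixes a change of image with a change of position, and the CBCTs behind it leave out motion while the beam is on

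*Combined protocol and SAP*

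**What the plan says.** All references are to the combined protocol and SAP.

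- **Aim.** Exploratory objective 2.3.1 is "To quantify SBRT dose variation between planned and delivered with VRT-DIBH technique".
- **Planned dose.** Section 4.1: "The SOC DIBH CT scan will be transferred to Eclipse treatment planning system for treatment planning". Section 5.2.2 confirms the source: "The acquired high-resolution DIBH CT will be used as a primary image for planning". On contrast, section 5.2.1 says: "If there is no contraindication to contrast administration, patient will receive DIBH CT scans with contrast administration".
- **Delivered dose.** Section 5.2.8: "Project treatment beams on CBCT images and recalculate dose with CBCT images", and then "Evaluate dose difference between the planned and the delivered". Section 6.3 repeats that dosimetric accuracy will come from dose calculation on the CBCTs.
- **Timing of the CBCTs.** Section 5.2.5 has one before treatment and one before the last beam, "not during treatment beam delivery".
- **Interpretation.** Section 4.1: "These CBCT images will be used to evaluate treatment dose variation to quantify treatment delivery accuracy".

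Neither 5.2.8 nor 6.3 mentions a density calibration for CBCT, a density override, a contrast correction, a registration of planning-CT densities onto the CBCT, or a reference dose on the same type of image.

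**The concern.** A dose calculation depends on where the anatomy lies relative to the beams and on the densities read from the image. Between the planned and the delivered figure both change: the patient may have moved, and the image goes from a planning CT, usually with contrast, to a CBCT. Only the first change says anything about how well the breath-hold technique delivers the plan.

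The dose figure also rests on anatomy imaged between beams. Movement within a breath-hold, or from one hold to the next, while the beam is on does not enter it. Reporting the result as delivery accuracy would claim more than the calculation measures.

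At stake are objective 2.3.1, the dosimetric accuracy named as an aim in 6.1, and the dosimetric impact listed as a descriptive output in 6.2. Sections 6.0 and 6.2 also intend the descriptive statistics to help size a later trial. If dose deviation were used for that, a shift or spread that comes from the images would be carried forward.

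**Working it through.** The plan gives no figure to reproduce. It sets no tolerance, standard deviation or margin for the dose difference, and the 10 patients are expressly not justified statistically. The check is therefore to trace what feeds each side.

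**Step 1: split the difference.** Write D(densities; position) for the computed dose.

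- Planned dose = D(planning CT; planned position), from 4.1, 5.2.1 and 5.2.2.
- Delivered dose as planned in 5.2.8 and 6.3 = D(CBCT; CBCT position).

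Adding and subtracting D(planning CT; CBCT position) gives

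delivered − planned = [D(planning CT; CBCT position) − D(planning CT; planned position)] + [D(CBCT; CBCT position) − D(planning CT; CBCT position)].

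The first bracket is the position effect that objective 2.3.1 is after. The second is the image effect, including contrast. The plan computes only the sum, and the middle term needed to separate them appears nowhere.

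**Step 2: what averaging does.** Suppose the image effect has mean b over patients. The expected mean difference is then the true position effect plus b, whatever the number of patients. If a contrast-related part of size c is present only in a share p of patients, it adds pc to the mean and c√(p(1−p)) to the between-patient spread.

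**Step 3: illustration under assumptions.** The documents give neither b nor an SD. Take a true delivery difference of zero, a constant b of 0 to 3% of dose, and an SD of 2% or 4%. With 10 patients, the half-width of a 95% t interval is 2.262/√10 = 0.715 SD. The probability that the interval excludes zero, from the noncentral t distribution with 9 degrees of freedom and noncentrality (b/SD)√10, is:

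| b | SD 2% | SD 4% |
|---|---|---|
| 0 | 0.05 | 0.05 |
| 1% | 0.29 | 0.11 |
| 2% | 0.80 | 0.29 |
| 3% | 0.99 | 0.56 |

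The plan specifies descriptive statistics, with no such interval or test. The table shows only how readily an image effect could pass for a delivery error if b had a consistent sign.

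**Step 4: which motion enters which output.**

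| Data during a treatment session | Stated use | Enters the dose? |
|---|---|---|
| CBCT before treatment and before the last beam (5.2.5) | Position error and dose (5.2.8, 6.3) | Yes, as two between-beam snapshots per session |
| Imaging in two breath-hold periods during delivery (4.1) | Tumor position variation | No |
| AlignRT deltas during treatment (4.1, 5.2.8) | Surface stability and reproducibility | No |

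The study observes motion during treatment, but the dose figure does not use it.

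**The case against.** **Silence is not absence.** Section 5.2.4 gives treatment planning as standard of care, and 6.3 exports the CBCTs to dedicated software. A local density calibration or contrast override could exist unwritten and could shrink the image effect. This stands: the documents neither state nor exclude such a step, so a material bias is possible but not shown. It does not remove the point, because the recalculation on CBCT is a study analysis and 5.2.8 and 6.3 are where its method belongs.

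**The size is assumed.** A reader might infer that every patient's difference carries a same-sign error of a few percent. The documents do not support that. They give no density error, contrast is omitted where contraindicated, and lung and liver sites are mixed, so the effect may differ between patients in size and sign.

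**The study does look at motion during treatment.** A reader might infer that motion during the beam is missed altogether. It is not, as Step 4 shows; the gap is confined to the dose estimate. Nor can the two CBCTs be set against the camera rate of about 25 Hz in section 1.3: that is an imaging rate, and the documents do not say how often surface deltas are stored.

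**The output is exploratory.** Dose is not among the endpoints in 2.4, and the main feasibility question does not depend on it. This also stands and limits the weight of the point, although 6.1 to 6.3 still present dosimetric accuracy as a principal descriptive result.

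**Conclusion.** The point holds in a limited form. Followed as written, 5.2.8 and 6.3 yield a difference that combines image and contrast effects with true position change and omits beam-on motion, yet 4.1 reads it as delivery accuracy. The structural part follows from the text alone. The size and sign of the image effect cannot be derived from the documents; the figures in Step 3 are illustrations resting on an assumed constant bias and an assumed SD.

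The effect is confined to objective 2.3.1 and the dosimetric description in 6.1 to 6.3. The 50% feasibility criterion in 6.0 and the margin and surface-threshold objectives in 2.2 do not use this dose comparison. It is a worthwhile, inexpensive improvement to an exploratory result and no threat to the study's main conclusion.

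**What to change.** Change 5.2.8 and 6.3 as follows.

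1. **Make the primary dose deviation like-for-like.** Register the planning CT to each CBCT position, recalculate the treatment beams with the planning-CT densities, and subtract the planned dose. Both sides then share one density source, so contrast is common to both. If an override is used in planning, state it and apply it to both.
2. **Show the direct CBCT recalculation beside it.** The gap between the two is the image-type difference (the second bracket in Step 1), reported openly and kept out of the delivery result. State how CBCT densities were assigned.
3. **Rename the result** *dose on anatomy at CBCT time (between beams)* in place of delivered dose or delivery accuracy, and align the sentence in 4.1.
4. **Optional additions.** Pre-last-beam minus first-CBCT dose may be added as a measure of within-fraction change only. It drops the planned dose and cancels error already present at the first CBCT, so it cannot replace planned versus delivered. An isocentre-shift calculation may serve as a sensitivity analysis, preferably using the in-treatment tumor-position imaging. If AlignRT surface deltas are used, state that they are a surrogate for tumor position; the link between surface and tumor is itself under study in 4.1.

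The cost is revised analysis wording and some physics time. The core change uses images the protocol already acquires. Registration brings its own error, which should be reported with the result.

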5.3 Follow-up procedures

- No follow-up required for this study after radiation completed. Follow-up per standard of care for SBRT treatment per treating radiation oncologist.

5.4 Time and Events Table

	Pre-study	Treatment
Assessment		
Informed Consent	X	
History and PE ^A	X	X ^C
Pregnancy Test ^B	X	
CBCT scans		X

^A include vital signs

^B Recommended but patient may refuse if they attest they are not pregnant

^C Only vital signs, once per week

5.5 Removal of Subjects from Study

Subjects can be taken off the study treatment and/or study at any time at their own request, or they may be withdrawn at the discretion of the investigator for safety, behavioral or administrative reasons. The reason(s) for discontinuation will be documented and may include:

- 5.5.1 Subject voluntarily withdraws from treatment (follow-up permitted);
- 5.5.2 Subject withdraws consent (termination of treatment and follow-up);
- 5.5.3 Subject is unable to comply with protocol requirements;
- 5.5.4 Subject demonstrates disease progression (unless continued treatment with study drug is deemed appropriate at the discretion of the investigator);
- 5.5.5 Subject experiences toxicity from standard of care radiation treatment that the treating physician wants to stop the subject's continuation on the protocol
- 5.5.6 Treating physician judge's continuation on the study would not be in the subject's best interest;
- 5.5.7 Subject becomes pregnant
- 5.5.8 Development of second malignancy (except for basal cell carcinoma or squamous cell carcinoma of the skin) that requires treatment, which would interfere with this study;
- 5.5.9 Lost to follow-up.

